5.7. Laboratory, Vital Signs, Tanner Stage Assessment

For laboratory data, vital sign measurements and other continuous safety data, the number of observations, mean, standard deviation, median, minimum, maximum will be summarized by visit. Height, weight, BMI, and Tanner scores will be summarized using the number of observations, mean, standard deviation, median, minimum, and maximum by age group (ages 2-4, 5-11 and 12-17 years at start of parent study). The visits shown in these reports will be the baseline visit from the parent study, weeks 12, 24, 48, and 96, from the parent study and all visits from the extension study where

the data is collected. Some additional analyses of the Tanner data that takes age at time of measurement into account may also be done.

The Potentially Clinically Important (PCI) Flag is a derived flag value based on the PCI criteria defined for laboratory data captured in the study. The PCI criteria are based on NCI toxicity criteria. The number (%) of subjects with PCI events will also be provided for the lab data.

These summaries will be performed for FAS (active period (both parent and extension studies)), WAS, and RTAS.

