9.2. Efficacy Analysis

9.2.1. Analysis of Primary Endpoint

The primary endpoint in this study are related to safety. Efficacy endpoints are secondary.

9.2.2. Analysis of Secondary Endpoints for Subjects in the Active Treatment Period, and Withdrawal/Re-treatment Period

The secondary efficacy endpoints will be analyzed in the active treatment period and the withdrawal/re-treatment period. For the overall population as well as each of the JIA subpopulations, descriptive statistics will be provided for each study endpoint at all time points in the study. For categorical endpoints, the summary statistics will contain the frequency, percentage, and 95% confidence interval (CI) for the percentage. For continuous endpoints, the summary statistics will contain the number of observations, mean, standard

9.4.2. Safety Analysis for Subjects in the Active Treatment Period, and Withdrawal/re-treatment Period:

The occurrence of all adverse events (infectious and noninfectious), infections considered preventable by vaccination, and injection site reactions as well as treatment-emergent adverse events, potentially clinically important laboratory measurements, and premature discontinuations during the study will be summarized as using frequency and percentage, as well as adjusted rate per 100 subject-years of exposure to etanercept.

For laboratory data, vital sign measurements, and other continuous safety data, the number of observations, mean, standard deviation, median, minimum, maximum, and 95% CI of the mean will be summarized by visit for raw data and the change from baseline. Height, weight, BMI, and Tanner scores will be summarized using the number of observations, mean, standard deviation, median, minimum, and maximum by age group. Height, weight and BMI will also be compared with data from standardized growth charts.

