1. INTRODUCTION

[Note: In this document, any text taken directly from the protocol is italicized.]

The purpose of this document is to provide further details about the statistical analysis methods specified in the study protocol B1801023. *Protocol B1801023 is an 8-year extension study designed to further characterize the long-term safety profile, malignancy and other serious adverse events, and clinical benefit for those pediatric subjects who received at least one dose of etanercept and completed 96 weeks of investigational product and/or follow-up in study 0881A1-3338-WW (B1801014). The previous study was designed to assess the clinical benefit and the long-term safety of etanercept for 2 years (96 weeks) in pediatric subjects with extended oligoarticular juvenile idiopathic arthritis, enthesitis-related arthritis (ERA), or psoriatic arthritis (PsA).*

Based on the lack of information regarding when treatment with etanercept should be discontinued and the success of re-treatment if relapse occurs, this protocol is being amended to also explore clinical benefit and physical function after withdrawal of etanercept and after disease relapse occurs.

A brief description of the study objectives and the study design are given in [Section 2](#). Subsequent sections include the definitions of baseline, efficacy and safety endpoints, and analysis populations followed by details about statistical methods. Any major deviations from the methods specified in this document and the protocol must be discussed in the clinical study report.

In order to evaluate overall safety in the most meaningful way, data from the 8 year extension study should not be analyzed independent of the data collected during the preceding 2 year parent study. Therefore, most of the safety analyses will be based on the combined data from the parent study and the subsequent extension. The resulting data summaries and analyses will cover the entire period of up to 10 years. In some cases, in order to fully address the entire etanercept experience, data from subjects who were in the parent study but were never enrolled in the extension study will be included in determining overall rates. Details will be provided in the following sections.

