Tanner Stage Assessment for subjects <18 years of age or who have a score of <5 on 1 or more applicable domain(s). The Tanner Assessment does not need to be repeated if it was performed within 2 months before the early withdrawal visit.

Vital Signs: Temperature, blood pressure (mmHg) and pulse rate (beats/min, after sitting for at least 5 minutes);

Growth parameters: height, weight, BMI;

- Efficacy:
 - *ACR Pediatric 30, 50, 70, 90, and 100, defined as $\geq 30\%$ (and 50%, 70%, 90%, 100%, respectively) improvement from baseline in at least 3 of the 6 following variables, with no more than 1 of the remaining variables worsening by $> 30\%$:*
 - *Physician's Global Assessment (PGA) of Disease Activity on a 21-circle visual analogue scale (VAS);*
 - *Patient/Parent Global Assessment on a 21-circle VAS;*
 - *Childhood Health Assessment Questionnaire (CHAQ)*

- *Number of joints with active arthritis, defined as joints that are swollen or, in the absence of swelling, joints with limited range of motion accompanied by pain and/or tenderness;*
- *Number of joints with limited range of motion;*
- *Laboratory measure of inflammation, c-reactive protein (CRP);*

(Note: ACRPedi responses will be calculated based on parent study baseline. For subjects aged ≥ 18 years, CHAQ is missing)

- *Individual components of the ACR Pediatric Assessments;*
- *Pain Assessment on a 21-circle VAS;*
- *Duration of morning stiffness in minutes;*
- *Clinically inactive disease defined as follows per 2011 Wallace Criteria:*
 - *No joints with active arthritis (defined as joints that are swollen or, in the absence of swelling, joints with limited range of motion accompanied by pain and/or tenderness);*
 - *No fever, rash, serositis, splenomegaly, or generalized lymphadenopathy attributable to JIA;*
 - *No active uveitis;*
 - *CRP level within normal limits in the laboratory where tested or, if elevated, not attributable to JIA;*
 - *PGA of disease activity score of best possible on the scale used;*
 - *Duration of morning stiffness of ≤ 15 minutes;*
- *The Juvenile Arthritis Disease Activity Score (JADAS), using 4 components (PGA of Disease Activity, Patient/Parent Global Assessment, number of joints with active arthritis and CRP).*

- *Additional Secondary Endpoints for ERA Subjects*
 - *Overall Back Pain and Nocturnal Back Pain on a 100 mm VAS;*

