5.8. Growth Parameters

Height, weight, and body mass index (BMI) will also be compared with data from standardized growth charts. Height, weight, and BMI will be summarized using Z-scores. Z-score is calculated using the following formulation:

$$Z = \frac{(X / M)^L - 1}{LS}, L \neq 0$$

Or

$$Z = \ln(X / M) / S, L = 0$$

where X is the physical measurement (eg, height, weight, BMI) and L, M, and S are the values from standardized growth charts provided by the US Centers for Disease Control website (<http://www.cdc.gov/GrowthCharts/>) by gender for children from birth to 240 months. The Z-score cannot be calculated if age > 240 months.

These summaries will be performed for FAS (active period (both parent and extension studies)), WAS and RTAS.

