5.9. Efficacy Endpoints

Descriptive summary statistics will be provided for efficacy endpoints. For continuous endpoints, the summary statistics at each visit will include the number of observations, mean, standard deviation, median, minimum, maximum and 95% confidence interval for the mean. These statistics will be provided for the observed value and change from baseline. The mean percent change from baseline will be provided also. For categorical endpoints, the summary statistics will contain the frequency, percentage, and 95% confidence interval (CI) for the percentage.

These summaries will be performed for:

- FAS, active period data (both parent and extension studies. Baseline of parent study will be used for calculation of change from baseline). The reports will show the baseline (no baseline for ACRPedi responses), weeks 12, 24, 48, and 96 from the parent study and all visits from the extension study where data is collected.
- WAS. The reports will show all visits where data is collected.

- RTAS. Re-treatment period baseline will be used for calculation of change from baseline. The reports will show all visits where data is collected.

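### SAP 5.7 omits, without explanation, the change from baseline and its 95% CI that protocol 9.4.2 specifies for laboratory and vital-sign data

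*SAP*

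**What the plan says.** Protocol 9.4.2 covers laboratory data, vital signs and other continuous safety data. After the usual descriptive statistics, its list ends: "maximum, and 95% CI of the mean will be summarized by visit for raw data and the change from baseline".

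SAP 5.7 covers the same data and stops earlier: "the number of observations, mean, standard deviation, median, minimum, maximum will be summarized by visit". It adds a threshold count for laboratory data only: "The number (%) of subjects with PCI events will also be provided for the lab data". It applies these summaries to the FAS active period (parent and extension studies), the withdrawal analysis set (WAS) and the re-treatment analysis set (RTAS).

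For continuous efficacy endpoints, SAP 5.9 keeps both items. It lists a 95% CI for the mean and says: "These statistics will be provided for the observed value and change from baseline". CRP falls under that section, because SAP 4.2.2 lists "Individual components of the ACR Pediatric Assessments" among the efficacy endpoints and CRP is one of them.

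Growth has its own treatment in SAP 5.8: "Height, weight, and BMI will be summarized using Z-scores". On duration, the SAP introduction says: "The resulting data summaries and analyses will cover the entire period of up to 10 years".

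**The concern.** The primary endpoint of this study is a safety endpoint, and laboratory evaluations are a listed secondary endpoint. Yet the within-subject summary is kept for efficacy and missing for safety.

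The group measured at a late visit is not the group measured at baseline. Subjects who stop drug may move to the observational period, whose schedule has no laboratory tests or vital signs. Others enter the withdrawal period, where measurements continue but belong to WAS and no longer to the FAS active-period table. Entry there depends on inactive disease or a good response, so leaving the active-period table need not be random.

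A table of raw visit values then cannot show whether a liver enzyme, a blood count, blood pressure or pulse shifted in the subjects measured. In WAS and RTAS the natural question is what changes after drug is stopped or restarted, and that question is about within-subject change.

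**Working it through.** The plan states no figure for these data, so there is nothing to reproduce. The check is a comparison of the texts, one identity and an illustration.

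**1. Texts side by side**

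| Item | Protocol 9.4.2 | SAP 5.7 | SAP 5.9 (efficacy) |
|---|---|---|---|
| n, mean, SD, median, minimum, maximum by visit | yes | yes | yes |
| 95% CI of the mean | yes | no | yes |
| Change from baseline | yes | no | yes |

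The gap does not extend to height, weight, BMI or Tanner scores. Protocol 9.4.2 itself plans neither change nor CI for those.

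**2. What can be rebuilt from the SAP 5.7 tables**

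The CI of a raw mean can be. Its half-width is 1.96 × SD/√n, and n and SD are both reported:
- n = 100: 1.96/10 = 0.196 SD
- n = 50: 0.277 SD
- n = 30: 0.358 SD

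The CI of a change cannot be. With equal SDs its half-width is 1.96 × SD × √(2(1 − ρ))/√n, and the within-subject correlation ρ is not reported. At n = 100:
- ρ = 0.3: 0.196 × √1.4 = 0.232 SD
- ρ = 0.9: 0.196 × √0.2 = 0.088 SD

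The mean change itself cannot be rebuilt either, because

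visit mean − baseline mean of all = mean change in those measured + (baseline mean of those measured − baseline mean of all).

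The term in brackets is the case-mix shift, and SAP 5.7 reports nothing that gives it.

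**3. Possible size of the case-mix term (assumed inputs)**

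The documents give no drop-out rate or correlation for these data. Assumptions:
- no drug effect;
- each subject has a stable level plus visit noise, with ρ = 0.5 or 0.7;
- the chance of staying falls with the stable level (logistic, slope 1 per SD);
- 70% or 50% are retained;
- a common ageing drift of 0, 0.5 or 1.0 SD;
- 400,000 simulated subjects.

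| Ageing drift (SD) | ρ | Retained | Visit mean − baseline mean (SD) | Mean change in those measured (SD) |
|---|---|---|---|---|
| 0 | 0.5 | 70% | −0.18 | 0.00 |
| 0 | 0.7 | 70% | −0.21 | 0.00 |
| 0 | 0.5 | 50% | −0.29 | 0.00 |
| 0 | 0.7 | 50% | −0.35 | 0.00 |
| 0.5 | 0.5–0.7 | 50–70% | 0.16 to 0.32 | 0.50 |
| 1.0 | 0.5–0.7 | 50–70% | 0.66 to 0.82 | 1.00 |

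The change summary removes the drop-out artefact under this mechanism. It leaves the whole ageing drift in place.

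**4. Baselines**

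SAP 5.4 names withdrawal-period and re-treatment-period baselines, but SAP 5.7 does not use them. SAP 3.2 and 3.3 limit WAS and RTAS to data collected in their own period. The re-treatment assessment visit is in the protocol's withdrawal schedule, and the first re-treatment visit is Month 3. Read literally, RTAS holds no value from before drug is restarted. For subjects who come from active treatment, the pre-withdrawal value is taken at the active treatment early withdrawal visit, and the first withdrawal visit is at 1 month.

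**The case against.** Several points stand against a strong version of this concern.

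- **Authority.** Protocol section 9 lets the SAP modify its plans and requires an amendment only for major changes to the primary endpoint or its analysis. A reader might infer a protocol breach; the documents do not support that. The SAP introduction does require major deviations to be discussed in the study report.
- **Ageing.** A reader might infer that restoring change from baseline would separate drug effect from ageing. It would not. The study has a single treatment and no control arm, and the last rows of the simulation show the drift carried over in full.
- **Other outputs.** Raw means are not all that is left. Medians, ranges and PCI counts remain. Clinically significant laboratory abnormalities are recorded as adverse events, and potential Hy's law cases are reported as serious adverse events. CRP has change and CI under SAP 5.9. These outputs would catch marked abnormalities. They would not describe moderate shifts, and vital signs have no PCI count.
- **Medians and ranges.** If drop-out removed a distinct high-value subgroup, the retained median and maximum would reveal it. Under the gradual selection simulated here the median moves with the mean (−0.17 to −0.34 SD with no drift), so that safeguard is partial.
- **Continued measurement.** Not everyone who stops drug is lost. Withdrawal-period subjects are measured at every visit, and the early withdrawal visit includes laboratory tests and vital signs. This limits the loss for the study as a whole, though not for the FAS active-period table.
- **The raw-mean CI.** Its omission costs little, since it can be rebuilt.

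**Conclusion.** The omission is real and unexplained. If SAP 5.7 is followed as written, the planned tables give no within-subject change for liver enzymes, blood counts, blood pressure or pulse, and it cannot be reconstructed from them. The substantive loss is the change and its CI.

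The size depends on how drop-out relates to the measured level, which the documents do not state. Under the assumptions above, the raw comparison is off by 0.18 to 0.35 SD. If drop-out is unrelated to the measured level, the expected error is zero.

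This is an unexplained narrowing of a secondary descriptive safety summary, worth correcting because the correction is cheap. It does not touch the primary endpoint, CRP or the growth and Tanner summaries.

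**What to change.** In SAP 5.7, add the by-visit within-subject change from baseline with the 95% CI of its mean, in subjects with both values, for laboratory and vital-sign data and any other continuous safety data apart from height, weight, BMI and Tanner scores. Otherwise, state why it was dropped.

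Name the baseline for each set:
- **FAS, active period:** parent-study baseline.
- **WAS:** the withdrawal-period baseline of SAP 5.4, taken at the active treatment early withdrawal visit or, for direct entrants, at the study baseline visit. The parent-study week 96 value serves where the protocol's 14-day rule waives repeat procedures.
- **RTAS:** the re-treatment-period baseline of SAP 5.4, taken at the re-treatment assessment visit.

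State in SAP 3.2 and 3.3 that the baseline value may come from a visit at or before period entry, so that the restriction to own-period data does not exclude it. SAP 5.9 names no baseline for WAS; the same sentence can settle that.

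The cost is SAP wording, a derivation rule for each baseline and extra columns in existing tables. No new data are needed. The study report should say that these changes still contain ageing; addressing that would need age-specific reference ranges or age-standardised values.

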7.1. Safety Assessments

For subjects in the active treatment period, and the withdrawal/re-treatment period, safety will be assessed using the following measures:

1. Physical examinations will be performed by a physician. Any clinically significant abnormalities or worsening of medical history conditions should be recorded on the source documents and the appropriate adverse event CRF.
 - The physical examination will include the Tanner Stage Assessment for subjects <18 years of age or who have a score of <5 on 1 or more applicable domain(s). The sexual maturity rating of each subject will be determined according to the criteria adapted from Tanner. Female subjects will be classified on a scale of 1 to 5 across the following 2 maturity domains: breast and pubic hair characteristics. Male subjects will be classified on a scale of 1 to 5 across the following 3 maturity domains: pubic hair, penis and testes characteristics.
2. Vital sign measurements will include temperature, blood pressure and pulse rate (after sitting for at least 5 minutes).
 - A sitting blood pressure will be obtained by qualified site personnel and should be taken using the same arm throughout the study. If possible, a different arm should be used for the collection of blood samples.
3. Height and Weight.
4. Subjects will be evaluated for adverse events (infectious and noninfectious), serious adverse events, malignancy, and medically important infections.

- Infectious and noninfectious adverse events will be recorded on separate CRFs.
 - Medically important infections are defined as infections that require parenteral anti-infective agents (IV, IM) and/or hospitalization.
 - Infections considered preventable by vaccination will be reported on the infectious adverse event CRF.
5. Injection site reactions (symptoms, action taken, number, and frequency) will be monitored throughout the study and will be graded for intensity according to the Symptom Occurrence Scale (Itching, Redness, Swelling, Pain, Ulceration). Injection site reactions need to be clearly differentiated from symptoms associated with the technique of administering subcutaneous injections (eg, physical injury to blood vessels).
6. Clinical laboratory evaluations including blood chemistry, hematology, and urinalysis.

For subjects in the observational period, safety will be assessed through collection of the following information via telephone contact:

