5. ANALYSIS METHODS

All analyses will be performed for the overall population as well as each of the 3 JIA subtypes.

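### The committed Tanner summary groups subjects by age at parent-study entry, so on its own it cannot show whether puberty is on time; the analysis by age at measurement should not stay optional

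*SAP*

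**What the plan says.** Tanner stage is a secondary endpoint in Protocol section 2.2.3 and SAP section 4.2.2. SAP section 5.7 sets the summary: "Height, weight, BMI, and Tanner scores will be summarized using the number of observations, mean, standard deviation, median, minimum, and maximum by age group". The groups are "ages 2-4, 5-11 and 12-17 years at start of parent study". The summary is given by visit: "The visits shown in these reports will be the baseline visit from the parent study, weeks 12, 24, 48, and 96" of the parent study, then every extension visit with data. It covers the FAS active period, the WAS and the RTAS. Protocol section 9.4.2 has the same by-age-group summary without defining the bands.

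On age at assessment the SAP says only: "Some additional analyses of the Tanner data that takes age at time of measurement into account may also be done". No method is given.

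The general stratification rule in SAP section 5 is "All analyses will be performed for the overall population as well as each of the 3 JIA subtypes"; sex is not named. On the domains, Protocol section 7.1 says "Female subjects will be classified on a scale of 1 to 5 across the following 2 maturity domains: breast and pubic hair characteristics". Boys are staged on pubic hair, penis and testes. The SAP does not say whether Tanner scores are tabulated by domain or combined.

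For the other growth measures, SAP section 5.8 says "Height, weight, and BMI will be summarized using Z-scores", using sex-specific growth charts up to 240 months of age. Tanner stage has no counterpart.

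**The concern.** The expected Tanner stage depends on age at assessment and on sex. A band defined by age at entry describes a subject's age less and less usefully as a study of up to ten years goes on, and a band several years wide can hold pre-pubertal and fully mature subjects at the same visit. A low value in such a cell may mean late puberty, or only that the subjects in it are young. The SAP applies the appropriate principle to height, weight and BMI, and for Tanner stage it names the relevant adjustment but does not commit to it. At stake is whether the only planned Tanner tables, in children treated long term, can be interpreted for pubertal timing.

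**Working it through.** The documents give no computed figure to reproduce. The check has three parts: age arithmetic, an identity, and an illustration on assumed inputs.

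**1. Age span of each band.** Inputs: the bands (SAP 5.7), 96 weeks in the parent study, and the extension visit month. 96 weeks = 96 × 7 / 365.25 = 1.84 years. Ages are taken as completed years, so 5-11 runs from 5 to just under 12, and any gap between the two studies is ignored. Age at a visit = age at entry + 1.84 + month/12.

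| Band (width) | Ext. baseline | Month 24 | Month 48 | Month 96 |
|---|---|---|---|---|
| 2-4 (3 y) | 3.8-6.8 | 5.8-8.8 | 7.8-10.8 | 11.8-14.8 |
| 5-11 (7 y) | 6.8-13.8 | 8.8-15.8 | 10.8-17.8 | 14.8-21.8 |
| 12-17 (6 y) | 13.8-19.8 | 15.8-21.8 | 17.8-23.8 | 21.8-27.8 |

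For the 5-11 band at Month 48: 5 + 1.84 + 4 = 10.8, and 12 + 1.84 + 4 = 17.8.

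WAS and RTAS visits count from withdrawal or the re-treatment assessment, so the spread there can be greater. At withdrawal Month 12, someone from the 5-11 band could be 5 + 1.84 + 0 + 1 = 7.8 years old (direct entry) or up to 12 + 1.84 + 7 + 1 = 21.8 (entry at extension Month 84). From age 18, only those with a domain below stage 5 are still assessed.

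**2. Identity.** If stage is a function of age minus delay, S = f(A − d), then ages A with a one-year delay and ages A − 1 with no delay give the same distribution of stage. The median, SD, minimum and maximum therefore separate the two no better than the mean does. Numerically, a 9-16 age range with a one-year delay and an 8-15 range with none differ by 0.0. This holds for any curve f and for every domain.

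**3. Illustration for the 5-11 band (assumed inputs, not from the documents).** Stage = 1 + 4 × (age − onset)/D, held between 1 and 5. D is 4 or 5 years. Girls' onset is at 10 or 11 years, and boys' onset is 0.5, 1 or 2 years later. Ages are uniform over the band and half the subjects are boys. The younger mix tilts the age density so that mean age falls by 7 × 0.5/6 = 0.58 years. Ranges cover all 12 combinations; every row below the first is a change from no delay.

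| | Month 24 | Month 48 |
|---|---|---|
| Mean stage, no delay | 1.90 to 3.05 | 2.91 to 4.16 |
| One-year delay | −0.38 to −0.57 | −0.53 to −0.57 |
| Younger mix, no delay | −0.26 to −0.44 | −0.28 to −0.41 |
| Same younger mix, boys-only domain | −0.17 to −0.44 | −0.31 to −0.44 |
| 80% boys instead of 50%, combined score | −0.08 to −0.34 | −0.07 to −0.34 |

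At both visits everyone in the band is under 18, so the rule on who is assessed removes nobody. At Month 96 only (18 − 14.84)/7 = 45% of the band would be under 18, so no Month 96 value is offered.

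**4. Role of sex.** Breast, penis and testes are single-sex domains; only pubic hair is scored in both sexes. The last row of the table therefore applies to pubic hair or to a combined score, and to nothing else. The younger-mix rows do not depend on sexes being combined: the effect is present in the boys-only domain too.

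**The case against.** Several points on the other side have force.

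- **Pooling of the sexes.** A reader might infer that girls and boys are averaged together. The documents do not say so; they only omit a sex split. If the tables are by domain, three of the four domains separate the sexes by themselves. This stands, and it limits the sex-mix problem to pubic hair or a combined score.
- **The plan sees the issue.** SAP 5.7 itself raises age at measurement. What remains is optional versus committed wording, for a descriptive secondary endpoint in a single-arm study whose primary endpoint is malignancy. Neither document states an objective or hypothesis about delayed puberty. This limits the weight of the point but does not make the committed table interpretable.
- **Other routes to detection.** Under Protocol 7.1, clinically significant findings at the physical examination, which includes Tanner staging, go on the adverse event form. A delay recognised by the investigator could therefore reach the adverse event tables. Height Z-scores are also planned. These are partial safeguards: the first depends on individual judgement, and neither summarises pubertal timing.
- **Size.** The stage curves are assumptions, and the identity holds by construction. Agreed. The age spans are the firm part.
- **A stage-count table also needs a comparator, and cells will be small.** Agreed. The fix therefore names a reference and uses 2-year bands.

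**Conclusion.** The point holds in a limited form. The committed Tanner summary, read on its own, cannot show whether puberty is on time, because within a band fixed at entry it mixes age with pubertal timing. The problem is clearest in the 5-11 band, which spans seven years and covers about 10.8 to 17.8 years at extension Month 48. It is weaker in the 2-4 band, which is three years wide, and in the 12-17 band, which is already 13.8 years or older at extension baseline.

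This conclusion rests on the SAP wording and the age arithmetic. The stage differences rest on assumed curves and show only that a modest change in age mix can be of similar order to a one-year delay.

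A reader might go further and infer that the study cannot detect delayed puberty at all. The documents do not support that: the optional analysis could resolve the question if it were done, and the data for it are collected. This is a worthwhile, inexpensive improvement to a secondary safety analysis. No dose, visit or clinical rule is involved.

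**What to change.** In SAP 5.7:

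1. Keep the by-age-group summary, since Protocol 9.4.2 calls for it, and state that it is given by Tanner domain.
2. Replace the optional sentence with a committed table: for each domain, the number and percentage at each stage, by sex and age at assessment in 2-year bands, overall for the FAS active period. State which assessment counts when a subject has two in one band.
3. For the WAS and RTAS, give the same table where numbers allow, and otherwise a listing.
4. Name a published age- and sex-specific Tanner reference against which the table will be read.

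The cost is a SAP edit and one additional table from sex, date of birth and Tanner data already collected. The downsides are small cells, with about 100 subjects expected, and subjects who appear in more than one age band, so the bands are not independent. Both are acceptable in a descriptive table if footnoted.
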